Protocol Title

High-Dose Vitamin D3 in the Treatment of Human Immune Deficiency Virus Patients, A Double-Blind Randomized Control Trial

Protocol Version: 1.0

Date: August 15, 2019

Institute of Social & Cultural Studies
University of the Punjab,
Lahore

Abstract

Human immunodeficiency virus is a key challenge for global health. Vitamin D deficiency is common in people living with HIV infection. Antiretroviral therapy may create unique risk factors for vitamin D insufficiency, including alterations of vitamin D metabolism by ART.

The objective of the study is, to know the effect of high dose Vitamin D, in the treatment of HIV patients with antiretroviral therapy. It will be a randomized controlled trial, in which 104 patients visiting Said Mitha Teaching Hospital Lahore will be included.

The patients will be divided into two groups. Group-A patients will receive ARV + Vitamin D supplements and patients in Group-B will receive only antiretroviral therapy and placebo.

Methods/design: A randomized placebo double blind control trials of patients with age 19-50 years will be the participants of our study at VCCT center of said Mitha Teaching Hospital, located in walled city of Lahore, Pakistan. Participants will be randomly allocated to receive 25 hydroxyvitamin D supplementation (n=) or placebo (n=) with the start of ART.

The primary outcome will be achieved with high dose of serum 25-hydroxyvitamin D level at 24 weeks. Secondary outcome will include decrease in viral load, increase mean CD4 count to reduce prevalence of clinical symptoms (elevated levels of LFTs, decrease HB level & serum calcium level). Purposive sampling will be carried out.

Data will be collected through Performa, which will be entered and statistically analyzed, using SPSS version 24.0, This Performa is designed by the Punjab AIDS Control Programme including socio-demographic information, Pretest

information, posttest information & follow up chart. Chi-square test will be used to estimate the association among qualitative variables.

Discussion: High dose Vitamin D supplementation in HIV-infected patients has not previously been investigated in Pakistan and it is unknown whether increasing levels is associated with improved clinical outcome or not. Therefore, it is significant to conduct a study to know the effect of vitamin D in the treatment of HIV patients with antiretroviral therapy.

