2. RESEARCH OBJECTIVE

2.1 Primary objectives:

1. To determine whether proposed oral high dose vitamin D3 is sufficient for achieving the physiological concentration in HIV positive patients on ART. (primary outcome)

2.2 Secondary objectives:

1. To determine whether this intervention also improves CD4 count, viral load count, liver enzyme in study participants. (Efficacy outcome).
2. To discover whether this interventional regimen is safe and well tolerated by study participants. (Safety outcome).
3. To ascertain socio-demographics factors responsible for decreased level of vitamin D3 in HIV positive patients on ART.

2.3 Tertiary objectives:

1. To conclude the effects of total leucocytes count in HIV patients with vitamin D supplementation.
2. To determine the effects of total neutrophil count in HIV patients with vitamin-D supplementation.
3. To investigate the effects of total basophil count in HIV patients with vitamin-D supplementation.
4. To determine the effects of total eosinophil count in HIV patients with vitamin-D supplementation.
5. To conclude the effects of total monocyte count in HIV patients with vitamin-D supplementation.
6. To establish the effects of total platelets count in HIV patients with vitamin-D supplementation.
7. To find out the effects of total hemoglobin count in HIV patients with vitamin-D supplementation.
8. To determine the effects of total lymphocytes count in HIV patients with vitamin-D supplementation.

3. Study Population

Patients who visited the VCCT center of GOVT Said Mitha Teaching Hospital Lahore and the treatment center of Jinnah hospital HIV clinic were the study population and they were HIV positive and on ART. The study population consisted of HIV patients ranging in age from 19 to 50 years. Patients with severe vitamin D3 deficiency were seen at the multi-centric outpatient HIV department.

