4. STUDY PROCEDURES

4.1 Study Population

Patients visiting Said Mitha Teaching Hospital Lahore will be the study population and having diagnosed with HIV positive patients.

4.2 Sampling technique:

Random list was generated for the double blind purpose. This list was generated through Excel sheet.

4.3 Ethical Consideration:

The study will be conducted after approval from the Punjab University Ethical Review Board. Permission will also be obtained from Punjab AIDS Control Programme to use health facilities and this study will be registered at Clinical Trial.gov, to use the health facilities and services of paramedics staff for data collection. Written consent of parents and guardians will be taken before starting the study.

4.4 Data Collection:

All staff involved in the study will be trained by the principal investigator before start of data collection. Trained laboratory technician will screen the patients aged 19 years to 50 years of age in (VDT) diagnostic center of hospital visiting outpatients department in their community and will refer the positive patients to treatment center of AIDS Control Programme clinic of Mayo Hospital Lahore, After receiving their prescribed ART, the two positive groups would be divided into two equal groups, one group will receive 25hydroxy vitamin –D and other halves will receive placebo at the same time once weekly for 12 weeks. Patients will be called for follow-up after every

4 weeks. At the end, we will perform posttest and check the level of 25 hydroxy in both groups and other parameters and by using logistic regression we will evaluate the results of effectiveness of 25 hydroxyin blood levels of HIV patients

4.5 Randomization:

The random allocation sequence will be generated in an excel spread sheet by a statistician who will be independent of the study. Consecutive numbers will be assigned to active vs. placebo in equal numbers. No restrictions (e.g. stratification, block size) will be applied. This sequence will be used by the study pharmacy to label pairs of syringes containing active and placebo medication with a study number assigned to active and placebo arms, respectively. These staff will assign the consecutive ID numbers to participants according to the sequence in which they are enrolled, and the hospital pharmacy then supply syringes of placebo active medication bearing this ID number.

4.6 Blinding:

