3.1 Sample size calculation

Assuming that 60% of patients in the control arm would attain > 30% of their baseline vitamin-D status at 6 months, we calculated that a total of 94 participants (47 per arm) would need to complete follow-up in order to detect a 25% absolute increase (to 85%) in the proportion of patients attaining > 30% vitamin-D level at 6 months in the intervention arm with 80% power at the 5% significance level. (Lake, Vitamin D in HIV-Infected Patients on HAART, 2014).

This number was inflated to a total of 114 to allow for attrition due to death and loss to follow-up. No interim analysis was performed. (Shriver, 2019)

4. Aims and objectives:

Primary objectives

1. To determine whether proposed oral high dose vitamin D3 is sufficient for achieving the physiological concentration in HIV positive patients on ART. (primary outcome)

Secondary objectives

1. To determine whether this intervention also improves CD4 count, viral load count, liver enzyme in study participants. (Efficacy outcome).
2. To discover whether this interventional regimen is safe and well tolerated by study participants. (Safety outcome).
3. To ascertain socio-demographics factors responsible for decreased level of vitamin D3 in HIV positive patients on ART.

Tertiary objectives:

1. To conclude the effects of total leucocytes count in HIV patients with vitamin D supplementation.
2. To determine the effects of total neutrophil count in HIV patients with vitamin-D supplementation.
3. To determine the effects of total eosinophil count in HIV patients with vitamin-D supplementation.
4. To conclude the effects of total monocyte count in HIV patients with vitamin-D supplementation.
5. To establish the effects of total platelets count in HIV patients with vitamin-D supplementation
6. To find out the effects of total hemoglobin count in HIV patients with vitamin-D supplementation
7. To determine the effects of total lymphocytes count in HIV patients with vitamin-D supplementation
8. To see if the effects of total HCT count in HIV patients with vitamin-D supplementation

5. Outcomes

This section will present the outcomes investigated to answer the study aims and objectives. The analyses are described in section 6 Analyses.

5.1 Primary outcome:

1. To determine whether proposed oral high dose vitamin D3 is sufficient for achieving the physiological concentration in HIV positive patients on ART. (primary outcome)

5.2 Secondary outcomes:

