1. To determine whether this intervention also improves CD4 count, viral load count, liver enzyme in study participants. (Efficacy outcome).
2. To discover whether this interventional regimen is safe and well tolerated by study participants. (Safety outcome).
3. To ascertain socio-demographics factors responsible for decreased level of vitamin D3 in HIV positive patients on ART.

5.3 Tertiary outcome:

1. To conclude the effects of total leucocytes count in HIV patients with vitamin D supplementation.
2. To determine the effects of total neutrophil count in HIV patients with vitamin-D supplementation.
3. To determine the effects of total eosinophil count in HIV patients with vitamin-D supplementation.
4. To conclude the effects of total monocyte count in HIV patients with vitamin-D supplementation.
5. To establish the effects of total platelets count in HIV patients with vitamin-D supplementation
6. To find out the effects of total hemoglobin count in HIV patients with vitamin-D supplementation

7. To determine the effects of total lymphocytes count in HIV patients with vitamin-D supplementation
8. To see if the effects of total HCT count in HIV patients with vitamin-D supplementation

Other blood laboratory parameters

Vitamin-D level, CD4 count, viral Load, PCR, CBC

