6.1 Populations

Intention-to-treat (ITT)

All randomised study subjects. This will be seen as the primary population for the analysis.

Per Protocol (PP)

All randomised study subjects completing the whole study period (complete cases). For a specific analysis, study subjects with missing data on any of the variables in the model will be excluded from the analysis. Analyses of this population is seen as a sensitivity analysis to investigate whether conclusions are sensitive to assumptions regarding the pattern of missing data.

6.2 Groups:

Patients with with vitamin-D deficiency are divided into two groups i.e placebo group and vitamin-D group.

Placebo group: out of total 95 participants 47 participants were on placebo arm

Vitamin-D group:

Similar out of total 95 participants 48 participants were on vitamin-D arm

Vitamin-D deficiency:

All randomized study subjects will be divided into two subgroups according to having vitamin-D deficiency at baseline visit.

Division of groups:

All randomised study subjects will be divided into two subgroups according to treatment.

7. Analyses

All outcomes will be presented using descriptive statistics. As the sample size is low so we will check the normality of each variable on screening (Visit 1) and according to the normality check we will determine the mean difference change in Placebo and active treatment arm.

In descriptive analysis we will mention the mean value of each variable with lower and upper bound with 95% confidence interval, 5% trimmed mean, median, Std. Deviation as per the each group ; normally distributed data by the Mean, Variance, Standard deviation (SD), lower and upper values of the variables to see the outliers if any.

In analytical analysis we will apply T-Test for two independent samples to see the difference between two arms. In case any variable doesn't follow the normality assumptions, we will use non-parametric test.

For the safety objective we will use only frequency/number of events to present it.

SPSS 21 will be used for all statistical analysis.

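### The SAP's tertiary outcome lists replace the protocol's basophil count with haematocrit without a stated reason, and a change after allocation cannot be excluded

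*SAP*

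**What the plan says.** Protocol 2.3 sets out eight tertiary objectives, all blood counts. Item 3 is "To investigate the effects of total basophil count in HIV patients with vitamin-D supplementation". Haematocrit does not appear there.

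The SAP gives its tertiary list twice, as objectives in section 4 and as outcomes in section 5.3. Both versions have eight numbered items, neither includes basophils, and item 8 in both is "To see if the effects of total HCT count in HIV patients with vitamin-D supplementation". HCT is read here as haematocrit.

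SAP 7.3 applies one analysis to all tertiary objectives: mean change from Visit 1 to Visit 4, compared between arms by a two-sample t-test or Mann-Whitney U test, with a 95% confidence interval. It names no individual count, so the lists in sections 4 and 5.3 decide what is tested.

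Three other places bear on the matter. Under SAP 5.3, a line of other laboratory parameters reads "Vitamin-D level, CD4 count, viral Load, PCR, CBC", with no components of the blood count named. SAP 6.2 gives arm sizes in the past tense: "out of total 95 participants 47 participants were on placebo arm" and "out of total 95 participants 48 participants were on vitamin-D arm". SAP 3.1 adds "No interim analysis was performed".

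**The concern.** A SAP may add detail to the protocol's endpoints. If it removes one or adds another, it should say so and say when. Here a reader of the SAP alone would take haematocrit as planned from the start and would not know that basophils had been. Because both documents list eight items, the exchange is easy to miss.

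Timing gives the point its weight. An outcome list altered before any data by arm exist is an ordinary revision. If it is altered afterwards, the choice of outcomes may depend on the results. Part of this SAP contains arm sizes that could be known only after allocation, and nothing in the available text shows that the outcome list was settled before then. What is at stake is whether the tertiary results can be presented as a prespecified set.

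**Working it through.** **1. Item-by-item comparison.**

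| Tertiary item | Protocol 2.3 | SAP 4 and 5.3 |
|---|---|---|
| Leucocytes | item 1 | item 1 |
| Neutrophils | item 2 | item 2 |
| Basophils | item 3 | absent |
| Eosinophils | item 4 | item 3 |
| Monocytes | item 5 | item 4 |
| Platelets | item 6 | item 5 |
| Haemoglobin | item 7 | item 6 |
| Lymphocytes | item 8 | item 7 |
| Haematocrit | absent | item 8 |

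Seven items are shared, one appears only in the protocol and one only in the SAP: 7 + 1 + 1 = 9 distinct outcomes. The change removes 1/8 = 12.5% of the protocol's tertiary list. Both SAP lists run from 1 to 8 with no gap, so a line lost in text conversion is not a likely explanation.

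**2. What SAP 6.2 shows about timing.** The plan's own figure comes first. SAP 3.1 assumes 60% against 85%, 80% power and a 5% level. Taking the test as two-sided (not stated) with unpooled variance, n per arm = (1.960 + 0.842)² × (0.60 × 0.40 + 0.85 × 0.15) / 0.25² = 46.2, rounded up to 47, or 94 in all. This matches SAP 3.1, which then inflates the total to 114.

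The arm sizes in SAP 6.2 are 47 + 48 = 95. That is neither 94 in equal arms nor 114, so they are not the planning figures. It is one more than the required completers and 95/114 = 83.3% of the recruitment target. The 95 may therefore be completers rather than everyone randomised; the SAP does not say. Either way, that paragraph was written after allocation.

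**3. What SAP 6.2 does not show.** It dates its own paragraph, not the lists in sections 4 and 5.3. SAP 3 still describes recruitment of 114 patients as future and leaves both arm sizes blank, so parts of the SAP appear to come from different times. Nor does tense put the documents in order. The protocol is marked "Date: August 15, 2019", yet its section 4.2 reports a completed step, "Random list was generated for the double blind purpose", while its section 4.5 puts generation of the sequence in the future.

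**4. Effect on the number of tests.** The count stays at eight. If each were tested at 5% and the tests were independent, the chance of at least one false positive would be 1 − 0.95⁸ = 0.337 with either list. Blood counts are correlated, so this is only illustrative. The exchange does not change the overall error rate; it changes which outcome is tested.

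**The case against.** A reader might infer that the tertiary set was changed after allocation. The documents do not support that, for the reasons in step 3 of the working. In addition, the opening part of the SAP was not in the text available for this review. A date, version or change note could stand there, and its absence cannot be held against the plan.

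A reader might also infer that selective reporting has taken place or that the change was concealed. Neither is supported. A plan contains no results, knowing arm sizes is not the same as knowing basophil or haematocrit values by arm, and an equal item count is no evidence of intent. A drafting slip is as consistent with the text as a deliberate choice.

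Nor can it be said that basophils will never be analysed. The complete blood count is listed as a laboratory parameter, and SAP 7 promises descriptive statistics for all outcomes. Since the components are not named, basophils are neither clearly included nor clearly excluded. What is lost is the named between-arm comparison.

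Finally, the consequence is small: one item in the lowest tier. All of this stands, and it limits the size of the point. It does not remove the mismatch, which appears in both SAP lists and is unexplained in the available text.

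**Conclusion.** The mismatch is certain: basophils are out, haematocrit is in, and the other seven items agree. Under SAP 7.3 this takes a between-arm comparison away from a planned outcome and gives one to an outcome the protocol does not name. Because SAP 6.2 was written after allocation, a change to the list after allocation cannot be excluded, but it is not shown. The point is therefore a risk of selective outcome reporting, not a finding of it.

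Its size is one of eight tertiary outcomes replaced. The primary outcome, the secondary outcomes, the sample size and the number of tertiary tests are unchanged. The conclusion assumes that HCT means haematocrit and that no explanation stands in the part of the SAP not seen. If a dated explanation does stand there, the timing question may be answered, and what remains is to carry it into the outcome lists.

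**What to change.** - Restore basophil count to the tertiary lists in SAP 4 and SAP 5.3. SAP 7.3 needs no edit, because it already covers every tertiary objective.
- Keep haematocrit, marked as added after protocol version 1.0, and spell out the abbreviation.
- Report all nine tertiary outcomes.
- State the date and reason for the change, and whether outcome data by arm had been seen by then. Call haematocrit post hoc only if it was added after that.
- Say in SAP 6.2 whether the 95 are participants randomised or participants who completed.

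The cost is a few lines of SAP text and one more analysis row. No new visit or blood draw should be needed. The complete blood count is scheduled at Visits 1 and 4 in both documents, and basophils are assumed to come with the differential already required for neutrophils, eosinophils and monocytes. With nine tests instead of eight, the illustrative figure under independence rises from 0.337 to 1 − 0.95⁹ = 0.370, a modest price in an exploratory tier for reporting the full set.

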5.4 Safety outcomes

Adverse events

Adverse events are reported from the visit 1 till Visit 5.

Concomitant medications

Usage of medications during study period will be recorded.

6. Populations and subgroups to be analysed

6.1 Populations

Intention-to-treat (ITT)

All randomised study subjects. This will be seen as the primary population for the analysis.

Per Protocol (PP)

All randomised study subjects completing the whole study period (complete cases). For a specific analysis, study subjects with missing data on any of the variables in the model will be excluded from the analysis. Analyses of this population is seen as a sensitivity analysis to investigate whether conclusions are sensitive to assumptions regarding the pattern of missing data.

6.2 Groups:

Patients with with vitamin-D deficiency are divided into two groups i.e placebo group and vitamin-D group.

Placebo group: out of total 95 participants 47 participants were on placebo arm

Vitamin-D group:

Similar out of total 95 participants 48 participants were on vitamin-D arm

Vitamin-D deficiency:

All randomized study subjects will be divided into two subgroups according to having vitamin-D deficiency at baseline visit.

Division of groups:

All randomised study subjects will be divided into two subgroups according to treatment.

7. Analyses

All outcomes will be presented using descriptive statistics. As the sample size is low so we will check the normality of each variable on screening (Visit 1) and according to the normality check we will determine the mean difference change in Placebo and active treatment arm.

In descriptive analysis we will mention the mean value of each variable with lower and upper bound with 95% confidence interval, 5% trimmed mean, median, Std. Deviation as per the each group ; normally distributed data by the Mean, Variance, Standard deviation (SD), lower and upper values of the variables to see the outliers if any.

In analytical analysis we will apply T-Test for two independent samples to see the difference between two arms. In case any variable doesn't follow the normality assumptions, we will use non-parametric test.

For the safety objective we will use only frequency/number of events to present it.

SPSS 21 will be used for all statistical analysis.

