7.1 Primary outcome

The primary outcome analysis will be performed to check the difference change in Placebo group and Active Treatment group (Vitamin-D Group) through comparing mean difference from Visit 1 to Visit 4. This test will identify the mean increase or decrease in the Vitamin-D levels in the study Participants.

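### The completer-based per-protocol set cannot test the missing-data assumption, because the ITT primary test is by inference already an observed-case analysis

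*SAP*

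**What the plan says.** SAP 6.1 defines two populations. ITT is everyone randomised and is primary; no missing-data rule is attached to it. Per-protocol is "All randomised study subjects completing the whole study period (complete cases"), and anyone missing a variable in a given model is left out of that model. The SAP describes the per-protocol run as a "sensitivity analysis to investigate whether conclusions are sensitive to assumptions regarding the pattern of missing data".

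SAP 7 compares the arms with an independent-samples t-test, or a non-parametric test if normality fails. SAP 7.1 applies this to vitamin D by "comparing mean difference from Visit 1 to Visit 4". Protocol section 7 instead plans a linear regression adjusted for baseline, also without a missing-data method. The visit tables in both documents schedule vitamin D only at Visit 1 and Visit 4 (week 12). Visit 5, the end of study, is at week 24.

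On numbers, SAP 3.1 states that "a total of 94 participants (47 per arm) would need to complete follow-up" and raises the total to 114 for death and loss to follow-up. SAP 6.2 reports that "out of total 95 participants 47 participants were on placebo arm", with 48 on vitamin D.

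**The concern.** A participant with no Visit 4 sample has no change score, so the ITT label cannot be honoured by the test as written. The analysis meant to show whether that matters is restricted to completers and excludes the same people. If the two results agree, a reader may take this as evidence that missing data do not matter, although nothing about the missing participants has been examined. Death and loss to follow-up, the reasons the SAP gives for attrition, may well be related to illness or to not taking study medication. Loss of that kind could bias both analyses in the same direction. Because per-protocol is defined by completeness, the plan also contains no result for participants who actually followed the protocol.

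**Working it through.** **Who enters each analysis**

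- Set A, the primary test: randomised participants with vitamin D at both Visit 1 and Visit 4.
- Set B, per-protocol: participants who completed the whole study (to Visit 5) and have no missing model variable. Every member of B is in A. The two differ only by people with a Visit 4 value who were lost between weeks 12 and 24.
- Randomised participants without a Visit 4 value are in neither set.

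Comparing A with B therefore only adds or removes people whose primary outcome is known. It makes no alternative assumption about those whose outcome is unknown.

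**How much missing data the plan expects**

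Inputs from SAP 3.1: 60% versus 85%, "with 80% power at the 5% significance level" (taken as two-sided), 1:1 allocation.

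n per arm = [p1(1−p1) + p2(1−p2)] × (1.960 + 0.842)² / (p2−p1)² = (0.2400 + 0.1275) × 7.849 / 0.0625 = 46.15, rounded up to 47, or 94 in total. The SAP's figure is reproduced. (With a pooled variance it would be 49 per arm.)

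Allowance for non-completion: 114 − 94 = 20, and 20/114 = 17.5%. If the 95 in SAP 6.2 are completers out of 114 randomised, which the SAP does not state, it is 19/114 = 16.7%.

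**Illustration on the responder scale**

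Assumptions: 57 randomised per arm; the 95 are the observed cases, so 10 placebo and 9 vitamin D participants are missing; completers respond at about the planned rates (0.60 × 47 ≈ 28; 0.85 × 48 ≈ 41). Pooled two-proportion z-tests:

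| Handling of the missing | Placebo | Vitamin D | Difference | z | p |
|---|---|---|---|---|---|
| Completers only | 28/47 = 59.6% | 41/48 = 85.4% | 25.8 points | 2.82 | 0.005 |
| All missing are failures | 28/57 = 49.1% | 41/57 = 71.9% | 22.8 points | 2.49 | 0.013 |
| Extreme bound: missing placebo succeed, missing vitamin D fail | 38/57 = 66.7% | 41/57 = 71.9% | 5.3 points | 0.61 | 0.54 |

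**Illustration on the ng/ml scale**

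This is closer to the SAP's test. Suppose vitamin D arm dropouts rise 5 to 15 ng/ml less than completers in that arm (an assumption; the documents give no figure), and placebo dropouts resemble placebo completers. The completer difference is then too large by (9/57) × gap: 0.158 × 5 = 0.8 ng/ml, up to 0.158 × 15 = 2.4 ng/ml.

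**The case against.** Several stronger readings are tempting, and the documents do not support them.

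- *The SAP says ITT drops people.* It does not. The exclusion sentence sits under per-protocol. That the ITT test is observed-case is an inference from the test chosen and the absence of any other rule. No other reading can be applied as written, so the inference stands, but it is an inference.
- *The two sets are identical and must agree.* Per-protocol requires completion to week 24 and the primary test only a week 12 value, so results can differ through losses in between. The sets overlap heavily; they need not coincide.
- *By the SAP's own count, 19 participants dropped out.* SAP 6.2 does not call the 95 completers, 114 is a recruitment target, and the protocol abstract gives 104. If only 95 were randomised, the 19 are unfilled places and the illustrations above lose their basis. The 17.5% allowance in SAP 3.1 does not depend on this.
- *The p-values show that the trial's result is fragile.* They test a responder rate taken from a 6-month sample-size assumption, whereas SAP 7.1 tests mean change to week 12. The last row of the table is a bound and not a forecast. Without a standard deviation or expected effect in ng/ml, the importance of a 0.8 to 2.4 ng/ml bias cannot be judged.

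There is also a fair objection to imputation as a remedy. With one scheduled post-baseline value, imputing from baseline alone adds almost nothing to a complete-case baseline-adjusted regression. Compliance is a single yes/no item on the research proforma. The visit tables schedule no interim vitamin D, although protocol section 5 mentions day 60. This stands. The part of the remedy that tests the assumption is the tipping-point or best/worst-case analysis.

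**Conclusion.** The concern holds in a limited form. As written, the primary analysis is by inference an observed-case analysis under an ITT label. The per-protocol set is the same set or a subset, so it cannot perform the sensitivity role that SAP 6.1 gives it. This is more than missing detail, because following the plan would produce a check that reassures without testing anything. The share of data at issue is 17.5% by the plan's own allowance, or 16.7% if the 95 are completers of 114 randomised. The illustrations show only that missingness on this scale could matter; they rest on the stated assumptions and do not predict this trial's result. The SAP should be corrected before the analysis is run.

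**What to change.** 1. **Primary analysis.** Name the baseline-adjusted linear regression already in protocol section 7, in all randomised participants, and state how missing Visit 4 values are handled. One option is multiple imputation by arm from baseline 25(OH)D, doses received and recorded compliance.
2. **Missing-data sensitivity analysis.** Replace the completer set with a delta-adjusted (tipping-point) analysis of all randomised participants: lower the imputed vitamin D arm values in steps and report where the conclusion changes. A best/worst-case analysis is an alternative, most naturally if a responder endpoint is also defined.
3. **Complete cases.** Keep this result, labelled as supporting.
4. **Per-protocol.** Define it by adherence and protocol deviations instead of completeness. This must wait until protocol sections 4.4, 4.7 and 6, which conflict on the dosing schedule, have been reconciled.
5. **Counts.** State in SAP 6.2 whether the 95 are randomised participants or completers, and report numbers randomised and numbers with a Visit 4 value by arm.

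The cost is SAP wording and modest programming, with no new data. Intervals may be slightly wider. Item 4 also depends on the separate work of reconciling the dosing passages.
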